**Start of intervention and possibility for delay of intervention**

If the time/hour of the day for visit 2 enables the subject to take two doses of the medication this day, the intervention may start on visit 2, which subtracts one day from the time schedule below.

For logistic reasons in the collaboration between the Department of Nuclear Medicine and the Department of Gastroenterology at the local study centre, the treatment start may be delayed for a maximum of seven days. In case the start is postponed, the postponed days are not counted as study days.

**Study Diary 2 – treatment period**

This diary registers the number of daily stools and consistency according to the Bristol stool form. The participants also note any AEs. The Study Diary 2 is commenced at Study Visit 2 and entails three periods

1. Study Visit 2 (Study day 8)
2. Run in period of five days (Study day 9 – 13)
3. Registration of Primary endpoint (Study day 14 – 20)

These periods are not separated in the diary. The diary also forms the subject's study participation card, with contact information to the relevant investigator or study nurse.

On study day 9, subjects set an "X" in the diary according to what treatment they think they are receiving: a) Colesevelam, b) Don't know, c) Placebo. This is used to assess initial blinding.

**Telephone consultation: Start of intervention****Study day 10**

The intervention has started on study day 9. The study nurse calls the subject to note possible early AEs, aid compliance, and to titrate the dose. If the nurse suspects an SAE, she contacts the investigator.

**Titration of intervention dose**

If the subject experiences lack of effect or the adverse symptoms constipation, vomiting, or nausea that could be caused by too high a dose of colesevelam the study nurse may taper or increase the daily dosage to three or one capsule(s) twice daily.

Whenever the dose is changed, a follow-up telephone consult is planned within 2–3 days.

## **Telephone consultation: Start of endpoint period – compliance and AEs**

### **Study day 14 ( $\pm$ 1 day)**

The study nurse calls the subject to note possible early AEs, aid compliance, and to titrate the dose if indicated. This consult is mandatory regardless of follow-up on any prior dose titration.

## **Study visit 3 – Treatment end and repeated questionnaires (Q-2)**

**Study day 21 (+1–3 days).** The treatment ends at the end of day 20.

Before (same day or 1-2 days ahead of) the clinical contact on visit 3, the investigator answers if he/she has had any contact with the subject, perhaps through the study nurse: yes/no. Further if yes, what he/she thinks the allocated treatment was: “a) Colesevelam, b) Don’t know, c) Placebo.

The (sub)investigator then in the order below:

- distributes repeated questionnaires (Q-int)
  - SF36v2, SHS, GSRS
    - If the subject participates in the voluntary questionnaire on HRQoL and sexual dysfunction, this questionnaire is distributed again by e-mail
  - In the questionnaire, the subject is asked to mark which treatment he/she thinks to have received. This will assess the maintenance of blinding.
- collects the Study Diary 2 and checks this for deficiencies
- obtains a history of AEs and deem if any AE the nurse has noted are related to the intervention, ie. AR. This can only be done by a doctor
- collects surplus medication, counts the number of return capsules and assess compliance
- orders follow up blood analysis to assess biochemical side effects (sampled in 3 – 4 days)
  - ALT, ALP, bilirubin, amylase,
- schedules study end telephone consultation
- confirms agreement for the six-month follow-up

The six-month follow-up is included in the study consent. This follow-up is identical to the one described above for subjects without diarrhoea.

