## Aims

1. To determine the efficacy and safety of colestevlam for treating bile acid diarrhoea (BAD).
2. To correlate both the current scintigraphic Selenium conjugated Tauro-homocholic acid retention test (SeHCAT) and the biochemical marker of BAD 7 $\alpha$ -hydroxy-4-cholesten-3-one (C4) with colestevlam treatment response, and to validate the cut-off values determined in the VABAD trial (1).

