### **Intervention:**

Colesevelam (tablets of 625mg) or identical placebo capsules. One to three capsules taken twice daily. Start dose is two capsules twice daily. The dose is titrated by a study nurse who is independent of the investigators.

Parallel arms of 12 days blinded treatment, of which the first five days is run-in and the last seven days measure endpoints.

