##### Tabulated list of adverse reactions

In controlled clinical studies involving approximately 1400 patients and during post-approval use, the following adverse reactions were reported in patients given Cholestagel.

The reporting rate is classified as very common ( $\geq 1/10$ ), common ( $\geq 1/100$  to  $< 1/10$ ), uncommon ( $\geq 1/1,000$  to  $< 1/100$ ), rare ( $\geq 1/10,000$  to  $< 1/1,000$ ), very rare ( $< 1/10,000$ ) and not known (cannot be estimated from the available data).

Nervous system disorders
Common: Headache
Gastrointestinal disorders
Very common: Flatulence*, constipation*
Common: Vomiting, diarrhoea*, dyspepsia*, abdominal pain, abnormal stools, nausea, abdominal distension
Uncommon: Dysphagia
Very rare: Pancreatitis
Not known: Intestinal obstruction*,**
Musculoskeletal and connective tissue disorders
Uncommon: Myalgia
Investigations
Common: Serum triglycerides increased
Uncommon: Serum transaminases increased

\* see section below for further information

\*\* adverse reactions from post-marketing experience

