**Study visit 2 – Assessment of eligibility by stool diary results**

**Study Day 8.** Concurrent with the second SeHCAT visit, all subjects meet in the fasting state, the only exception is drinking still water. Subjects must not ingest alcohol on the day before visit 2.

Fasting blood samples are drawn from all subjects, no later than 10:00 AM.

The blood samples include: 4mL plasma for C4 and for FGF19 analysis (total 8mL). Routine samples for: p-triglycerides, p-cholesterols (total, High and Low-Density Lipoproteins), fasting p-glucose.

Any violation of alcohol abstinence the day before study visit 2 and of pausing statin/fibrate use leads to exclusion as a protocol violation. Minor violations of fasting (drinking thin fluids like coffee or tea, also with milk added) are noted in the CRF and the patient can participate in the study. All other violations lead to exclusion or rescheduling for fasting blood sampling another day.

The (sub)investigator collects the baseline study diary and tallies this.

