## **End of the clinical study phase**

**Study day 26 ( $\pm$  3 days).** AE registration continues for minimum 72 hours after the end of treatment. Colesevelam is not absorbed from the gastrointestinal tract. Normal gastrointestinal transit is 36 – 48 hours leaving minimal if any traces of colesevelam at this time. If visit 3 (above) is scheduled after these 72 hours, the AE registration at visit 3 is final. The investigator may opt to only telephone the patient if an end-of-trial blood samples is abnormal. Otherwise the investigator telephones the subject (this also applies to subjects in open-label treatment):

- Assess biochemical AEs
  - Informs the subject of these results

- Takes a history of AEs
- Takes action if needed (blood sampling, extended AE registration etc.)

The blinding is not unveiled at this time.

The central study nurse notes what he/she thinks the treatment was (questions as above).

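### As scheduled, colesevelam's effect on triglycerides cannot be assessed, and the other four safety analytes can be compared between arms only off treatment

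*Combined protocol and SAP*

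**What the plan says.** Under Aims, the first objective is "To determine the efficacy and safety of colestevlam for treating bile acid diarrhoea (BAD". The Intervention section sets "Parallel arms of 12 days blinded treatment, of which the first five days is run-in and the last seven days measure endpoints".

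The section on study visit 3 places the visit at "Study day 21 (+1–3 days" and states that "The treatment ends at the end of day 20". At that visit the investigator "orders follow up blood analysis to assess biochemical side effects (sampled in 3 – 4 days". The panel is ALT, ALP, bilirubin and amylase. The same four are listed as baseline bloods in the Case Record Form section for visit 1.

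The tabulated adverse reactions give two entries under Investigations: "Serum triglycerides increased", graded common (at least 1/100 and below 1/10), and raised transaminases, graded uncommon. Triglycerides are drawn at visit 2, in the fasting state and before treatment: "Routine samples for: p-triglycerides, p-cholesterols (total, High and Low-Density Lipoproteins), fasting p-glucose". The Biochemistry section names triglycerides among the routine samples but leaves the timing to other sections. In the text, only visit 2 supplies one.

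The section on the end of the clinical study phase keeps adverse event registration open for at least 72 hours after treatment, and makes it final at visit 3 if that visit falls later than this. It puts a telephone call that reviews biochemical adverse events on day 26 ± 3. On residual drug it says: "Normal gastrointestinal transit is 36 – 48 hours leaving minimal if any traces of colesevelam at this time".

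**The concern.** The one planned laboratory safety sample seems to miss on both panel and timing. It leaves out the analyte that the protocol's own source says changes most often, although a fasting baseline for it is already collected. It is also taken after the point at which the protocol regards the drug as essentially gone, although the patient attends the clinic closer to the last dose.

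At stake is what the trial can say on laboratory safety under Aim 1. A statement that no laboratory effect was seen would carry no information on triglycerides, and for the other analytes it would describe patients after treatment. The endpoint and ancillary analysis sections specify no laboratory safety analysis that would make this limit visible to a reader.

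**Working it through.** **1. Treatment length.** Study Diary 2 puts run-in on days 9–13 and endpoint registration on days 14–20. That is 5 + 7 = 12 days, and 20 − 9 + 1 = 12, which reproduces the stated 12 days. The last treatment day is day 20.

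**2. Interval if the delay counts from visit 3** (the more natural reading, since the blood is ordered there). Sample day = visit day + 3 or 4; interval = sample day − 20.

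| Visit 3 on day | Sample on day | Days after last treatment day |
|---|---|---|
| 21 | 24–25 | 4–5 |
| 22 | 25–26 | 5–6 |
| 23 | 26–27 | 6–7 |
| 24 | 27–28 | 7–8 |

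The full range is 4 to 8 days.

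**3. Interval if the delay counts from the end of treatment.** Sample day = 20 + 3 or 4 = day 23–24, an interval of 3 to 4 days. This fits a late visit 3 poorly, because a sample ordered on day 24 would already be due or overdue. Neither reading gives an on-treatment sample. Starting treatment on visit 2 moves the schedule forward by one day and leaves the interval unchanged if the later days move with it.

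**4. What can be compared.**

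| Analyte | Before treatment | After treatment | Comparison available |
|---|---|---|---|
| ALT, ALP, bilirubin, amylase | Visit 1 | Follow-up sample | Between arms, off treatment |
| Triglycerides | Visit 2, fasting, statins/fibrates paused | None in the text | None |

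**5. Fit with the other windows.** The call can fall on day 26 − 3 = 23 to 26 + 3 = 29. Counting from visit 3, the sample falls on day 24–28, so a call on day 23 precedes every possible sample and a call on day 27 can still precede one. Registration need stay open only to the end of day 23 (20 + 3). A visit 3 on day 24 makes registration final, while the blood it orders is drawn on day 27–28, which is 3 to 4 days later.

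**6. What adding triglycerides would buy (illustration).** Assume half of the planned 170 patients receive colesevelam: 170 / 2 = 85. The chance of at least one event is 1 − (1 − p)^85. This is 57% at p = 1% and over 99.9% at p = 10%. Against an assumed placebo rate of 1%, power with 85 per arm is about 33% if the colesevelam rate is 5% and 73% if it is 10% (normal approximation, rough at such rates). The gain is mainly detection and description.

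**7. Interval if the blood is drawn at visit 3.** 21 − 20 = 1 to 24 − 20 = 4 days after the last treatment day.

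**The case against.** The Biochemistry section says that the routine analyses are not endpoints and accepts differences between site laboratories. They can be read as monitoring of individual patients, and the end-of-phase section allows further blood tests and longer registration where needed. No primary, secondary or ancillary endpoint depends on this sample.

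A reader might infer that Aim 1 cannot be answered at all for laboratory safety. The documents do not support that. The four panel analytes have values before and after treatment in both randomised arms. ALT bears on the other listed laboratory reaction and amylase on the listed pancreatitis. Clinical adverse event collection is largely untouched.

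A reader might also infer that short-lived changes will have resolved, so that the trial is bound to report no effect. The statement on transit concerns drug in the gut, not how fast an analyte returns to baseline, and no reversal times are given. Nor is it shown that every patient is off drug when sampled: the end-of-phase section mentions subjects in open-label treatment without explaining this.

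Finally, 1% to 10% of 85 gives 0.85 to 8.5, which invites the claim that 1 to 8 patients with a rise would be missed. That applies a band pooled from controlled studies and post-approval use to 12 days of exposure, with no threshold, exposure time or placebo rate for triglycerides.

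What the objection leaves standing is the missing post-treatment triglyceride value, the off-treatment timing and the conflicting windows. One reservation applies: the overview chart in Appendix 1 could not be read in the copy reviewed, so the finding on triglycerides rests on the text.

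**Conclusion.** The point holds in a limited form. On the text as it stands, the effect of colesevelam on triglycerides cannot be assessed, because there is a baseline and no later value. ALT, ALP, bilirubin and amylase can be compared by arm, but only after blinded treatment has ended: 4 to 8 days after the last treatment day on the natural reading, 3 to 4 days on the other. How much is lost by sampling then cannot be computed from the documents. The sample can also fall after registration is final, or after the call meant to review it.

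The conclusion assumes a visit 3 window of day 21 to 24 and no triglyceride sample in the overview chart. It does not touch the efficacy endpoints. It is a worthwhile and cheap improvement to safety ascertainment, not a defect that undermines the trial.

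**What to change.** - Draw the follow-up blood at visit 3, as early in its window as possible. Late visits would still be up to 4 days after the last treatment day.
- Add fasting triglycerides to that sample.
- Record fasting status and whether statins or fibrates have been restarted. The pause is required only between visits 1 and 2, so change within an arm could mix the effect of colesevelam with resumed lipid therapy.
- Specify the laboratory safety analysis: change from baseline by arm (visit 2 for triglycerides, visit 1 for the other four), with the between-arm comparison as the result.
- Reconcile the sampling day with the end of adverse event registration and the day 26 ± 3 call. If a delay is kept, say from which day it counts.

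If the present timing or panel is kept, state that triglycerides are not assessed after treatment and that the laboratory results describe the off-treatment state.

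The cost is protocol wording, one extra routine assay on blood already planned, and fasting attendance at visit 3; a separate sampling trip is saved. The trade-off is that a purely delayed change would be caught only by adverse event follow-up.

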## **End of the clinical study phase**

**Study day 26 ( $\pm$  3 days).** AE registration continues for minimum 72 hours after the end of treatment. Colesevelam is not absorbed from the gastrointestinal tract. Normal gastrointestinal transit is 36 – 48 hours leaving minimal if any traces of colesevelam at this time. If visit 3 (above) is scheduled after these 72 hours, the AE registration at visit 3 is final. The investigator may opt to only telephone the patient if an end-of-trial blood samples is abnormal. Otherwise the investigator telephones the subject (this also applies to subjects in open-label treatment):

- Assess biochemical AEs
  - Informs the subject of these results

- Takes a history of AEs
- Takes action if needed (blood sampling, extended AE registration etc.)

The blinding is not unveiled at this time.

The central study nurse notes what he/she thinks the treatment was (questions as above).

## Six-month follow-up

The local (sub)investigator notes the result of the diagnostic work-up of diarrhoea.

The questionnaires (SF36v2, SHS, GSRS) are distributed electronically. This questionnaire also asks if, what, and how any medicine against diarrhoea is taken.

If the subject has consented to answer the questionnaires regarding sexual dysfunction these are also distributed via e-mail.

Analysis of primary and secondary endpoints does not wait until the follow-up is finished.

## Adverse events

All adverse events (AEs) and adverse reactions (ARs) are registered by an AE/AR table in the study Case Record Form and documented at study visits as specified above.

Serious AEs (SAE) and serious ARs (SAR) are defined as an AE or AR that is life-threatening or leading to death, that leads to hospitalization or prolonging of hospitalization, that causes seriously or sustained disability or incapacity to work, or causes a congenital anomaly.

All SAEs and SARs will be reported to sponsor as soon as possible and within 24 hours. A SAR that is not expected is deemed Suspected Unexpected SAR (SUSAR). If the event is life-threatening or deadly sponsor reports to the DMA and to the Ethical Committee immediately and within 7 days with follow up within further 8 days.

All other SUSARs are reported to DMA within 15 days of sponsors knowing.

A SAR is deemed SUSAR if not listed in the AE table for colesevelam.

All SAR's are reported to the DMA and the Ethical Committee in yearly reports and after study completion (sooner than 3 months from the last visit, last patient).

## Schedule

Inclusion starts in the second half of 2018 and is estimated to complete within 18 months. Primary data collection ends two weeks after the last participant is included. The questionnaire follow-up ends six months after this time point.

## Rights

Sponsor is senior author on the planned publications, and the coordinating investigator is the first author. All protocol authors and the site investigators as listed on page 1 and page 2 have had the

opportunity to comment and influence the protocol. These persons are authors on the planned main publication. All rights are specified in agreements between each study centre and Sponsor.

## Planned publications

The main publication reports the primary and secondary endpoints described above, and authorship is described in detail clinical trial agreements.

Secondary publications based on tertiary or ancillary endpoints and from the biobank for future scientific work will have at least one author from each study centre. Authorship is based on the Vancouver criteria.

## Ethics

The study is conducted in accordance with the Helsinki declaration with guidelines from the International Conference on Harmonization of Good Clinical Practice (ICH-GCP). The Danish Medicines Agency, DMA (*Lægemiddelstyrelsen*) is applied for permission to using colesevelam and placebo. The GCP units as specified on page 3 monitor the study.

Registers with personal data are subject to the Danish Data Protection Agency, and will be handled in accordance with "*Lov om behandling af personoplysninger*". Data registers are subject to the "*Region Sjællands paraplygodkendelse*" and are applied as such.

The study is registered in the ClinicalTrials.gov register.

Pregnant women are excluded. This study entices no significant risks or strain for the study subjects. The study gives crucial information on the correlation between both the SeHCAT scintigraphy and the biochemical diagnostics to the effect of colesevelam treatment. If our thesis is confirmed, bile acid diarrhoea may be diagnosed exclusively on basis of a blood test thus eliminating the need for radiation exposure and providing the possibility for easy and early diagnosis at local facilities thereby making it possible for many more patients to be identified and treated. Academically, it will be possible to re-examine individuals with BAD to describe changes over time. This improves the diagnostic algorithm and provides great benefit to both future patients and potentially also to study subjects.

We offer subjects reimbursement for documented extra expenses for transportation.

## Recruiting

Patients referred for SeHCAT at study centres are eligible. Referring doctors/investigators may hand out the written information directly or (sub)investigators at SeHCAT centres may send the written invitation alongside the SeHCAT appointment. The potential participants are given the folder: "*Forsøgspersoners rettigheder i et sundhedsvidenskabeligt forskningsprojekt*". (Your rights as a participant in a research project). They are informed that this enquiry is regarding a medical scientific study, that participation is voluntary, and that it will have no influence on current and future examinations and treatment, whether the patient decides to participate in the study or not.

## Information and consent

The potential participant is invited to bring a bystander to the first SeHCAT day. A sub-investigator asks for interest in participation or in an information meeting, which then is arranged on the same day. The meeting is held in an office without time constraints. The written material is explained and questions are answered. It is the responsibility of the investigator (doctor) that the potential participant understands the information and is qualified for giving informed consent. If the potential participant after the information meeting need further time for reflection a maximum of 24 hours may be given. Informed consent is given on the criteria above. The doctor signs to guarantee this.

Participation is voluntary and consent may be withdrawn at any time with no reason given.

Consent for biological material for the biobank is given separately on the same occasion.

Likewise regarding consent for the investigator to contact the referring institution.

If the study reveals important information on the health of the subjects, he or she is informed unless the subject in the informed consent specifically wished not to be informed.

## Results

Upon conclusion of the study participants are offered a short synopsis of its results in plain Danish. Participants may beforehand decline to this. All data and information are kept in accordance with: "Lov om behandling af personoplysninger" and "Lov om patienters retsstilling".

The results - positive, negative or inconclusive - will be published in international peer-reviewed journals.

## Risks and nuisances

In total 50 mL full-blood is drawn with routine sterile technique and this is not considered a risk.

Colesevelam is well known as an off-label treatment for BAD. Common side effects are headache and constipation (10%) but it is generally well tolerated. See full description of side effects above.

Longtime treatment with colesevelam may give malabsorption of fatty nutrients and vitamins, but this is irrelevant in the short context of this study.

